11.2 Assessments performed only at screening and/or baseline

Assessments performed only at screening (Week -6/Week -2) and/or baseline (Week 0) include: assessment of eligibility criteria (including review of scores on the C-SSRS screening version), demographics, medical history, height and weight, and BSA affected by AD. These are described in further detail in Sections 11.2.1 to 11.2.5.

Laboratory tests performed only at screening/baseline include serology (hepatitis B and C, and HIV) and serum pregnancy test (Section 11.4.4).

11.2.1 Columbia-Suicide Severity Rating Scale

The C-SSRS screening version is a rater-administered instrument used to assess severity of suicidal ideation and suicidal behaviour through a series of simple, plain-language questions (26). The C-SSRS must be completed at screening to check that exclusion criterion no. 24 does not apply. Further details on the assessment according to the C-SSRS are included in the efficacy assessment & C-SSRS manual.

11.2.2 Demographics

The following demographic data will be recorded:

- Year of birth.
- Age.
- Sex (determined by the investigator): female, male.
Sex (female, male) refers to biological differences: chromosomes, hormonal, profiles, internal and external sex organs. Gender is a social criterion, e.g. feminine, masculine, and will not be captured.
- Confirmation of race and ethnic origin.

11.2.3 Medical and surgical history

Relevant past and concurrent medical/surgical history must be recorded and includes:

- All past and current skin disease history, including but not limited to:

- Alopecia.
- Vitiligo.
- Herpes simplex.

For each condition or diagnosis, the start date and stop date will be recorded (it will also be recorded if the diagnosis is ongoing).

- Atopy history, including:

- Duration of AD in years.
- Previous AD treatments.
- Asthma.
- Food allergy.
- Hay fever.
- Allergic conjunctivitis.
- Atopic keratoconjunctivitis.
- Eczema herpeticum.

- Other medical and surgical history including concurrent diagnoses.

For each condition, diagnosis, or surgical procedure, the start date and stop date will be recorded (it will also be recorded if the condition, diagnosis, or surgical procedure is ongoing).

Relevant medical history also includes diseases which are specifically listed as exclusion criteria and diseases for which specific treatments are listed as exclusion criteria.

11.2.4 Height and weight

The subject's height (without shoes) will be measured; the subject's weight (in indoor clothing and without shoes) will be measured.

11.2.5 Body surface area involvement

The total BSA affected by AD will be assessed by the investigator for each section of the body as component A of SCORAD (Section 11.3.3) and will be reported as a percentage of all major body sections combined. The following body regions will be assessed (brackets show the highest possible score for each region): head and neck (9%), anterior trunk (18%), back (18%), upper limbs (18%), lower limbs (36%), and genitals (1%). The total BSA score will be assessed according to the schedule of procedures in Section 4.

11.3 Efficacy assessments

11.3.1 Investigator's Global Assessment

The IGA is an instrument used in clinical trials to rate the severity of the subject's global AD and is based on a 5-point scale ranging from 0 (clear) to 4 (severe disease) (Panel 6). The IGA score will be assessed according to the schedule of trial procedures (Section 4). The assessment will be based on the condition of the disease at the time of evaluation and not in relation to the condition at a previous visit. Whenever possible, the IGA should be assessed by the same investigator at each visit to reduce inter-rater variability. The disease severity assessment score will be recorded in the eCRF.

Panel 6: Investigator's Global Assessment

Score	Disease severity	Standard IGA scale	IGA morphological descriptors
0	Clear	No inflammatory signs of atopic dermatitis.	No erythema and no elevation (papulation/infiltration).
1	Almost clear	Just perceptible erythema, and just perceptible papulation/infiltration.	Barely perceptible erythema and/or minimal lesion elevation (papulation/infiltration) that is not widespread.
2	Mild disease	Mild erythema and mild papulation/infiltration.	Visibly detectable, light pink erythema and very slight elevation (papulation/infiltration).
3	Moderate disease	Moderate erythema and moderate papulation/infiltration.	Dull red, clearly distinguishable erythema and clearly perceptible but not extensive elevation (papulation/infiltration).
4	Severe disease	Severe erythema and severe papulation/infiltration.	Deep/dark red erythema, marked and extensive elevation (papulation/infiltration).

11.3.2 Eczema Area and Severity Index

The EASI is a validated measure used in clinical practice and clinical trials to assess the severity and extent of AD (27). The EASI score will be assessed according to the schedule of trial procedures (Section 4). The assessment will be based on the condition of the disease at the time of evaluation and not in relation to the condition at a previous visit. Whenever possible, the EASI score should be assessed by the same investigator at each visit to reduce inter-rater variability.

The EASI is a composite index with scores ranging from 0 to 72, with higher values indicating more severe or more extensive condition. The index will be calculated as shown in Panel 7. Briefly, the investigator will assess the severity of 4 AD disease characteristics (erythema, induration/papulation, excoriation, and lichenification) on the 4 body regions (head/neck, trunk, upper extremities, lower extremities); severity will be assessed according to the scale shown in Panel 8. For each body region, a severity sum score will be calculated, which will be multiplied by an area score (Panel 8) and by a weighting factor. The EASI score equals the sum of the scores obtained for each body region (Panel 7).

The body region, severity of the disease characteristics (erythema, induration/papulation, excoriation, and lichenification), and the area score will be recorded in the eCRF.

Panel 7: Calculation of EASI

Body region	Erythema	Induration/ papulation	Excoriation	Lichenification	Area score	Weighting factor	Score
Head/neck	(SS +	SS +	SS +	SS)	x AS	x 0.1	
Trunk	(SS +	SS +	SS +	SS)	x AS	x 0.3	
Upper extremities	(SS +	SS +	SS +	SS)	x AS	x 0.2	
Lower extremities	(SS +	SS +	SS +	SS)	x AS	x 0.4	
The EASI score is the sum of the 4 body region scores							(range 0-72)

Abbreviations: AS, area score; EASI, Eczema Area and Severity Index; SS, severity score.

Modified from [\(28\)](#).

Panel 8: EASI severity score scale and area score scale

Severity score scale		Area score scale	
0	None/absent	0	0% affected area
1	Mild	1	1% to 9% affected area
2	Moderate	2	10% to 29% affected area
3	Severe	3	30% to 49% affected area
Note: half-steps (0.5, 1.5, 2.5) are allowed.		4	50% to 69% affected area
		5	70% to 89% affected area
		6	90% to 100% affected area

Abbreviations: EASI, Eczema Area and Severity Index.

11.3.3 Scoring Atopic Dermatitis

The SCORAD is a validated tool to evaluate the extent and severity of AD lesions, along with subjective symptoms [\(29\)](#). The maximum total score is 103, with higher values indicating more severe disease. SCORAD will be assessed according to the schedule of trial procedures (Section 4).

The assessment will be based on the condition of the disease at the time of evaluation and not in relation to the condition at a previous visit. Whenever possible, SCORAD should be assessed by the same investigator at each visit to reduce inter-rater variability.

The assessment consists of 3 components: A = extent, B = intensity, and C = subjective symptoms.

Extent (A)

The extent of AD is assessed as a percentage of each defined body area and reported as the sum of all areas (maximum score = 100%).

Intensity (B)

The intensity of 6 specific symptoms of AD (erythema, oedema/papulation, oozing/crusting, excoriation, lichenification, and dryness) is assessed by the investigator on an average representative area using the following scale:

0	=	None/absent
1	=	Mild
2	=	Moderate
3	=	Severe

Note: dryness is evaluated on uninvolved areas.

The sum of intensity score of the 6 symptoms will be reported (maximum score = 18).

Subjective symptoms (C)

A subjective assessment of the average itch and sleeplessness over the last 3 days/nights is recorded for each symptom by the subject on a visual analogue scale, where 0 is no itching (or no trouble sleeping) and 10 is unbearable itching (or lot of trouble sleeping), with a maximum possible score of 20.

The SCORAD is calculated as: A/5+7B/2+C.

The extent and intensity of disease will be reported in the eCRF.

11.3.4 Patient-reported outcomes

The following patient-reported outcomes will be assessed using an eDiary device:

- Eczema-related Sleep NRS (Section 11.3.4.1).
- Worst Daily Pruritus NRS (Section 11.3.4.2).
- Patient Days of Topical Treatment Use (Section 11.3.4.3).

At screening, the subjects will receive the eDiary device and eDiary training. The subjects must complete the eDiary in the morning each day as specified in the schedule of trial procedures (Section 4), and compliance with the eDiary completion will be reviewed by the trial site staff throughout the trial. The eDiary should be returned to the trial site as outlined in the schedule of trial procedures (Section 4).

In addition, the following patient-reported outcomes will be completed by the subjects at the trial site:

- DLQI (Section 11.3.4.4).
- POEM (Section 11.3.4.5).

An electronic device will be supplied to each trial site in which the subjects can complete the DLQI and POEM.

Each subject must make individual assessments relating to their perception of their disease and quality of life. These will be performed independently of the investigator and trial site staff, and prior to the investigator performing his/her efficacy assessments.

11.3.4.1 Eczema-related Sleep numeric rating scale

Subjects will rate how much their eczema interfered with their sleep over the last night using an 11-point NRS (Eczema-related Sleep NRS) with 0 indicating that it ‘did not interfere’ and 10 indicating that it ‘completely interfered’. Subjects will complete the Eczema-related Sleep NRS as part of the eDiary each day in the morning from Week -2 until Week 16.

11.3.4.2 Worst Daily Pruritus numeric rating scale

Subjects will assess their worst itch severity over the past 24 hours using an 11-point NRS (Worst Daily Pruritus NRS) with 0 indicating ‘no itch’ and 10 indicating ‘worst itch imaginable’. Subjects will complete the Worst Daily Pruritus NRS as part of the eDiary each day in the morning from Week -2 until Week 16.

11.3.4.3 Patient Days of Topical Treatment Use

Subjects will assess their use of topical AD treatment over the past 24 hours using a response scale ('yes', 'no'). Subjects will complete the Patient Days of Topical Treatment Use as part of the eDiary each day in the morning from baseline (Week 0) until Week 16.

11.3.4.4 Dermatology Life Quality Index

The DLQI is a validated questionnaire with content specific to those with dermatology conditions. It consists of 10 items addressing the subject's perception of the impact of their skin disease on different aspects of their HRQoL over the last week such as dermatology-related symptoms and feelings, daily activities, leisure, work or school, personal relationships, and the treatment (30). Each item is scored on a 4-point Likert scale (0 = 'not at all/not relevant'; 1 = 'a little'; 2 = 'a lot'; 3 = 'very much'). The total score is the sum of the 10 items (range: 0 to 30); a high score is indicative of a poor health-related quality of life. The DLQI will be completed at the trial site according to the schedule of trial procedures (Section 4).

11.3.4.5 Patient-Oriented Eczema Measure

The POEM is a validated questionnaire used to assess disease symptoms in atopic eczema patients in both clinical practice and clinical trials (31). The tool consists of 7 items each addressing a specific symptom (itching, sleep, bleeding, weeping, cracking, flaking, and dryness). Subjects will score how often they have experienced each symptom over the previous week on a 5-point categorical response scale (0 = 'no days'; 1 = '1 to 2 days'; 2 = '3 to 4 days'; 3 = '5 to 6 days'; 4 = 'every day'). The total score is the sum of the 7 items (range: 0 to 28) and reflects disease-related morbidity; a high score is indicative of a worse disease severity. The POEM will be completed at the trial site according to the schedule of trial procedures (Section 4).

11.4 Safety assessments

11.4.1 Vital signs

Vital signs (resting blood pressure, pulse, and body temperature) must be assessed according to the schedule of trial procedures (Section 4). Vital signs will be measured in a supine or sitting position following at least 5 minutes of rest.

For the first 3 IMP administration visits (i.e. at Weeks 0, 2, and 4), the subjects will be monitored after each IMP administration for immediate drug reactions for a minimum of

30 minutes with vital signs taken at 30 minutes or until stable, whichever is later (Section 9.2.1).

If an abnormal vital sign at screening is considered to be clinically significant by the investigator, it will be at the discretion of the investigator if the subject should be randomised into the trial (respecting exclusion criterion no. 26).

In case of abnormal findings, the vital sign measurement can be repeated approximately 15 minutes later with subjects resting in a supine or sitting position to verify the first measurement. Should the repeated measurement result in a normal value, the measurement must be repeated once more. If the third measurement verifies the second (normal) value, the first measurement should be considered false and the second measurement should be recorded in the eCRF. If the third measurement confirms the first measurement (abnormal), the second measurement will be considered false and the first measurement should be recorded in the eCRF.

Reporting in eCRF

The vital signs (and the time they were measured, when applicable) will be recorded in the eCRF; if vital signs were not assessed, a reason should be given. Clinically significant abnormal vital signs at the screening visit will be documented as medical history in the eCRF. At subsequent visits, any clinically significant deterioration of a pre-existing condition as well as any new clinically significant sign, symptom, or illness will be reported as an AE in accordance with Section 13.3.

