9.2 Administration of trial products

9.2.1 Administration of IMP

IMP administration visits are shown in the schedule of trial procedures (Section [4](#)). The IRT will assign the required IMP kit number for each subject at each IMP administration visit.

The first day of IMP administration is considered Day 0 (Week 0; Visit 3), where each subject will receive 4 SC injections (each 1.0 mL) of 150 mg tralokinumab or placebo to receive a total loading dose of 600 mg tralokinumab or placebo.

At subsequent visits in the treatment period, each subject will receive 2 SC injections (each 1.0 mL) of 150 mg tralokinumab or placebo every 2 weeks to receive a total dose of 300 mg tralokinumab Q2W or placebo Q2W. The last IMP administration will occur at Week 14.

The IMP will be administered by a qualified, unblinded healthcare professional (HCP); see Section [9.3.1](#) for blinding details. A minimum interval of 7 days is required between 2 administration visits.

The injections will be administered into the SC tissue of the upper arm, anterior thigh, or abdomen, separated by at least 3 cm. The injection site must be recorded in the source documents and in the eCRF at each IMP administration visit (Section [9.8.4](#)).

Further details on IMP administration are provided in a trial product handling manual. The IMP administration must be carried out according to these instructions.

LEO Pharma does not have any specific treatment recommendations in relation to overdose. The investigator will use clinical judgement to treat any overdose, if necessary. See Section [13.6.2](#) for further details regarding overdose.

Monitoring after IMP administration

For the first 3 IMP administration visits (i.e. Weeks 0, 2, and 4), each subject will be monitored after the IMP administration for immediate drug reactions for a minimum of 30 minutes with vital signs taken at 30 minutes or until stable, whichever is later. Vital signs will be documented in the eCRF (Section [11.4.1](#)).

As with any antibody, allergic reactions to dose administration are possible. The World Allergy Organization has categorised anaphylaxis into 2 subgroups: allergic anaphylaxis

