Appendix 5: Guidance for anaphylaxis diagnosis (24)

The National Institute of Allergy and Infectious Diseases (NIAID) and Food Allergy and Anaphylaxis Network Guidance for Anaphylaxis Diagnosis (FAAN) define anaphylaxis as a serious allergic reaction that is rapid in onset and may cause death. They recognise 3 categories of anaphylaxis, with criteria designated to capture from 80% of cases (category 1) to >95% of all cases of anaphylaxis (for all 3 categories).

Clinical criteria for diagnosing anaphylaxis

Anaphylaxis is highly likely when any one of the following 3 criteria are fulfilled:

- 1) Acute onset of an illness (minutes to several hours) with involvement of the skin, mucosal tissue, or both (e.g. generalized hives, pruritus or flushing, swollen lips-tongue-uvula).

AND AT LEAST ONE OF THE FOLLOWING:

- Respiratory compromise (e.g. dyspnea, wheeze-bronchospasm, stridor, reduced peak expiratory flow [PEF], hypoxemia).
- Reduced blood pressure (BP) or associated symptoms of end-organ dysfunction (e.g. hypotonia [collapse], syncope, incontinence).

- 2) Two or more of the following that occur rapidly after exposure to a likely allergen for that patient (minutes to several hours):

- Involvement of the skin-mucosal tissue (e.g. generalized hives, itch-flush, swollen lips-tongue-uvula).
- Respiratory compromise (e.g. dyspnea, wheeze-bronchospasm, stridor, reduced PEF, hypoxemia).
- Reduced BP or associated symptoms (e.g. hypotonia [collapse], syncope, incontinence).
- Persistent gastrointestinal symptoms (e.g. crampy abdominal pain, vomiting).

- 3) Reduced BP after exposure to known allergen for that patient (minutes to several hours):

- Infants and children: low systolic BP (age specific) or greater than 30% decrease in systolic BP.
- Adults: systolic BP of less than 90 mm Hg or greater than 30% decrease from that person's baseline.

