6.7.2 Vital signs

Vital signs will be summarised and listed.

For the summary tables of vital signs by visit, the last pre-dose vital sign assessment will be presented. If no dosing occurs at a visit, the last assessment recorded at the visit will be presented.

For the first 3 IMP dosing visits, subjects will be monitored after IMP administration for immediate drug reactions for a minimum of 30 minutes with vital signs taken at every 30 minutes or until stable, whichever is later. These measurements will be listed.

Potentially clinically significant values will be defined as displayed in [Table 2](#).

Table 2: Potentially clinically significant vital signs values

Protocol parameter	SI unit	PCS low	PCS high
Systolic blood pressure	mmHg	<90 and decrease from baseline ≥ 20	≥ 180 and increase from baseline ≥ 20
Diastolic blood pressure	mmHg	<50 and decrease from baseline ≥ 15	≥ 105 and increase from baseline ≥ 15
Pulse	beats/min	<50 and decrease from baseline ≥ 15	≥ 120 and increase from baseline ≥ 15

Trial ID: LP0162-1343	Date: 15-Jun-2021	Version: 1.0 Page 16 of 22
-----------------------	-------------------	-------------------------------

Abbreviations: PCS=potentially clinically significant.

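### The vital-signs repeat rule in Protocol 11.4.1 does not exempt post-injection readings, so a short-lived abnormal value can be labelled false and replaced by a normal one in the eCRF

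*Protocol*

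**What the plan says.** Protocol 11.4.1 sets out the repeat procedure for abnormal findings in three steps.

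- The repeat is optional: "the vital sign measurement can be repeated approximately 15 minutes later".
- A normal second reading triggers a compulsory third: "Should the repeated measurement result in a normal value, the measurement must be repeated once more".
- The third reading decides. If it is normal, "the first measurement should be considered false and the second measurement should be recorded in the eCRF". If it is abnormal, "the second measurement will be considered false and the first measurement should be recorded in the eCRF".

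The same section, like Protocol 9.2.1, requires subjects to be watched for immediate drug reactions after the first three IMP administrations, "with vital signs taken at 30 minutes or until stable, whichever is later". Section 9.2.1 sends these readings to the eCRF with a cross-reference to 11.4.1. Protocol 5.5 names this post-dosing monitoring as a precaution against hypersensitivity reactions.

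SAP 6.7.2 builds the by-visit tables at dosing visits from the last pre-dose assessment. Of the post-dose readings it says only: "These measurements will be listed". Table 2 of that section defines potentially clinically significant values but does not say whether post-dose readings are checked against them.

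**The concern.** For a reading taken before dosing, a value that two repeats fail to reproduce may reasonably be put down to error. After an injection the same pattern (abnormal, then normal, then normal) is also what a brief reaction that resolves would look like. Monitoring until stable presupposes that readings may change and that the change is informative. The repeat rule takes the change as proof that the first reading was wrong.

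At stake is the numerical record of the monitoring that the protocol set up for this purpose. If the abnormal value never reaches the eCRF, nobody reading the listing can see that it occurred, when it occurred or how far the value moved. Calling the reading false may also make an investigator less inclined to judge it clinically significant, and that judgement is what AE reporting depends on.

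**Working it through.** No sample-size, power or error-rate figure bears on this point, and the plan gives no figure to reproduce. The check is to trace the rule through each sequence of readings and follow the result into the outputs.

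**Does the rule reach post-dose readings?** It opens with abnormal findings in general. The paragraph just before it, on the randomisation decision, is expressly limited to screening; the repeat rule has no such limit. Post-dose monitoring is described in the same section, and 9.2.1 points back to that section for eCRF entry. No text exempts it.

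**What is recorded?** (A = abnormal, N = normal, in order of measurement)

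| Sequence | eCRF entry under 11.4.1 |
|---|---|
| A, no repeat | A stands |
| A, A | no explicit instruction; nothing makes the first reading false |
| A, N, A | first reading (A); the second is deemed false |
| A, N, N | second reading (N); the first is deemed false |

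The abnormal value is lost in one path only, A-N-N, and only if the investigator chose to repeat.

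**Timeline after an injection.** The monitoring reading falls at 30 minutes. An optional repeat comes about 15 minutes later, so at roughly 30 + 15 = 45 minutes. The third reading has no stated interval. An abnormality present at 30 minutes, gone by about 45 and still absent at the third reading therefore meets the protocol's description of a false reading. The value entered is the normal one from about 45 minutes. This can arise at three visits per subject (Weeks 0, 2 and 4).

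**Where the loss shows.**

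- By-visit summaries at dosing visits: unaffected, because they use pre-dose values.
- Post-dose listing: the abnormal value is missing.
- Table 2 flags: any flag that would rest on that value is missing, if Table 2 applies to post-dose readings at all. The SAP does not say.
- AE tables: the event appears if the investigator judged the sign clinically significant. Protocol 11.4.1 requires such signs to be reported as AEs after screening, and 13.2 asks the investigator to record observed changes that the subject does not report.

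**A related mismatch.** The protocol has vital signs taken at 30 minutes or until stable; SAP 6.7.2 has them taken at every 30 minutes or until stable. These imply different numbers of expected readings, so the listing's content is not settled.

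**The case against.** The strongest reply is that the rule was written for verification at screening. It follows the screening paragraph, not the monitoring paragraph, and its stated purpose is to verify the first measurement. Post-dose monitoring has its own procedure and its own statement that vital signs go into the eCRF, times are recorded where applicable, and the SAP speaks of the post-dose measurements in the plural. On that reading all post-dose values are kept. This is a fair reading of intent, but nothing in the text tells a site to adopt it, and a site following the general wording would replace the value.

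Other parts of the reply stand and limit the point:

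- A reader might infer that every recovering post-dose abnormality is lost. It is not: repeating is optional, and an unrepeated abnormal value stands.
- A reader might infer that the rule only ever overturns abnormal values. It does not: a normal second reading is itself overturned if the third is abnormal.
- A reader might infer that a real reaction vanishes from the safety data. The rule governs which number is entered. AE reporting of clinically significant signs does not depend on the repeat.
- A reader might set the rule against the adult blood-pressure threshold in Appendix 5 ("systolic BP of less than 90 mm Hg or greater than 30% decrease") and infer that anaphylaxis could go unrecorded. That threshold belongs to the criterion requiring exposure to a known allergen for that patient. In the other two criteria reduced blood pressure counts only alongside other features, such as skin or respiratory involvement, which are themselves reportable.
- A reader might infer bias towards no difference between arms. Post-dose values feed only a listing, and Protocol 14.3.5 plans no formal testing, so no affected comparison can be named.
- A reader might model the loss. If each reading is independently abnormal with assumed probability p, every abnormal is repeated and A-A is kept, the recorded rate is p × [p + (1 − p)p] = p²(2 − p). That gives 0.0025 × 1.95 = 0.49% for p = 5%, and 0.01 × 1.90 = 1.9% for p = 10%. This describes random noise being filtered out, as intended; it does not measure lost reactions.

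**Conclusion.** The point holds as a narrow defect in data recording. As written, 11.4.1 allows a transient abnormal post-injection vital sign at Week 0, 2 or 4 to be labelled false and a later normal value to be entered instead. The rule cannot separate error from a short-lived reaction, and it conflicts with monitoring until stable. The SAP listing then loses the value, leaving AE reporting as the only explicit route into the safety data. Most exposed is an abnormality that the investigator does not judge clinically significant, or dismisses because the protocol calls it false.

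The conclusion assumes that the general wording is applied to post-dose readings and that the investigator chooses to repeat. No figure in the documents allows the number of affected readings to be estimated, and no between-arm summary is shown to be biased.

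**What to change.** In Protocol 11.4.1, limit the replacement of a reading deemed false to screening and pre-dose measurements. For post-dose readings at Weeks 0, 2 and 4, enter every measurement in the eCRF with its clock time, flag repeats, and let no later reading replace an earlier one.

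In SAP 6.7.2, list all of these readings and state whether the Table 2 criteria apply to them. Reconcile the protocol's and the SAP's wording on the 30-minute measurements so that both describe the same set of expected readings.

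The cost is protocol and SAP wording plus repeat rows on the eCRF vital-signs form, with no additional visits or procedures. The downside is that a few spurious readings will appear in the listing, where the times and repeat flags let a reader judge them.
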